### 10.2 Protocol Deviations and Amendments

The Investigator must adhere to the protocol as detailed in this document. The Investigator will be responsible for enrolling only those subjects who have met protocol eligibility criteria. The Investigators will be required to sign an Investigator Agreement to confirm acceptance and willingness to comply with the study protocol. The Investigator should document and explain any protocol deviations in source. The Investigator should promptly report any deviations to the Sponsor or designee, and to the IRB/EC in accordance with established IRB/EC policies and procedures. The Sponsor or designee will review all protocol deviations and conduct impact assessments as needed. As per the Sponsor's standard operating procedures, prospective requests

to deviate from the protocol, including requests to waive protocol eligibility criteria, are not allowed and will not be granted.

All protocol revisions (amendments) must originate with and be documented by the Sponsor. The Investigator must submit all amendments to his/her IRB for review and approval prior to implementation; documentation of approval signed by the chairperson or designee must be sent to the Sponsor.

### **10.3 Record Retention**

Essential documents should be retained for a minimum of 2 years after the last approval of a marketing application in an International Council for Harmonisation (ICH) region and until there are no pending or contemplated marketing applications in an ICH region or at least 2 years have elapsed since the formal discontinuation of clinical development of the investigational product. However, these documents should be retained for a longer period if required by the applicable local requirements. Essential documents include, but are not limited to, the following: signed informed consent documents for all subjects; subject identification code list, screening log (if applicable), and enrollment log; record of all communications between the Investigator and the IRB; composition of the IRB; record of all communications between the Investigator, Sponsor, and their authorized representative(s); list of Sub-Investigators and other appropriately qualified persons to whom the Investigator has delegated significant study-related duties, together with their roles in the study, curriculum vitae, and their signatures; copies of CRFs (if paper) and of documentation of corrections for all subjects; investigational product accountability records; record of any body fluids or tissue samples retained; and all other source documents (subject records, hospital records, laboratory records, etc.).

ICH requires that patient identification codes be retained for at least 15 years after the completion or discontinuation of the study.

### **10.4 Regulatory, Ethical, and Study Oversight Considerations**

#### **10.4.1 Regulatory and Ethical Considerations**

This study will be conducted in accordance with the protocol and with the following:

- Consensus ethical principles derived from international guidelines including the Declaration of Helsinki and Council for International Organizations of Medical Sciences (CIOMS) International Ethical Guidelines
- Applicable ICH Good Clinical Practice (GCP) Guidelines
- Applicable laws and regulations

The Protocol, Protocol Amendments, ICF, Investigator's Brochure, and other relevant documents (e.g., advertisements) must be submitted to an IRB by the Investigator and reviewed and approved by the IRB before the study is initiated.

Any amendments to the protocol will require IRB approval before implementation of changes made to the study design, except for changes necessary to eliminate an immediate hazard to study participants.

The Investigator will be responsible for the following:

- Providing written summaries of the status of the study to the IRB annually or more frequently in accordance with the requirements, policies, and procedures established by the IRB.
- Notifying the IRB of SAEs or other significant safety findings as required by IRB procedures.
- Providing oversight of the conduct of the study at the site and adherence to requirements of 21 Code of Federal Regulations (CFR), ICH guidelines, the IRB, European regulation 536/2014 for clinical studies (if applicable), and all other applicable local regulations.

#### 10.4.2 Financial Disclosure

Investigators and Sub-Investigators will provide the Sponsor with sufficient, accurate financial information as requested to allow the Sponsor to submit complete and accurate financial certification or disclosure statements to the appropriate regulatory authorities. Investigators are responsible for providing information on financial interests during the course of the study and for 1 year after completion of the study.

#### 10.4.3 Informed Consent Process

The Investigator or his/her representative will explain the nature of the study to the participant or his/her healthcare proxy and answer all questions regarding the study.

Patients must be informed that their participation is voluntary. Patients or their healthcare proxy will be required to sign a statement of informed consent that meets the requirements of 21 CFR 50, local regulations, ICH guidelines, Health Insurance Portability and Accountability Act (HIPAA) requirements, where applicable, and the IRB or study center.

The medical record must include a statement that written informed consent was obtained before the patient was enrolled in the study and the date the written consent was obtained. The authorized person obtaining the informed consent must also sign the ICF.

Patients must be re-consented to the most current version of the ICF(s) during their participation in the study.

A copy of the ICF(s) must be provided to the patient or the patient's healthcare proxy.

#### 10.4.4 Data Protection

Patients will be assigned a unique identifier by the Sponsor. Any participant records or datasets that are transferred to the Sponsor will contain the identifier only; patient names or any information which would make the participant identifiable will not be transferred.

The patient must be informed that his/her personal study-related data will be used by the Sponsor in accordance with local data protection law. The level of disclosure must also be explained to the patient.

The patient must be informed that his/her medical records may be examined by Clinical Quality Assurance auditors or other authorized personnel appointed by the Sponsor, by appropriate IRB members, and by inspectors from regulatory authorities.

#### 10.4.5 Dissemination of Clinical Study Data

A clinical study report (CSR) will be written after completion of the study.

It is anticipated that the results of this study will be presented at scientific meetings and/or published in a peer reviewed scientific or medical journal. The basic principles regarding publication of study results are as follows:

Both positive and negative study results will be disclosed. In general, the results of research will be submitted for publication to peer-reviewed scientific journals. These journals often do not consider negative results for publication. However, results will be otherwise disclosed on [www.clinicaltrials.gov](http://www.clinicaltrials.gov) as per regulatory requirement.

#### 10.4.6 Data Quality Assurance

All patient data relating to the study will be recorded on printed or eCRF unless transmitted to the Sponsor or designee electronically (e.g., laboratory data). The Investigator is responsible for verifying that data entries are accurate and correct by physically or electronically signing the eCRF.

The Investigator must maintain accurate documentation (source data) that supports the information entered in the eCRF.

The Investigator must permit study-related monitoring, audits, IRB review and regulatory agency inspections and provide direct access to source data documents.

Monitoring details describing strategy (e.g., risk-based initiatives in operations and quality such as Risk Management and Mitigation Strategies and Analytical Risk-Based Monitoring), methods, responsibilities and requirements, including handling of noncompliance issues and monitoring techniques (central, remote, or on-site monitoring) are provided in the Monitoring Plan.

The Sponsor or designee is responsible for the data management of this study including quality checking of the data.

The Sponsor assumes accountability for actions delegated to other individuals (e.g., contract research organization).

Study monitors will perform ongoing source data verification to confirm that data entered into the eCRF by authorized site personnel are accurate, complete, and verifiable from source documents; that the safety and rights of participants are being protected; and that the study is being conducted in accordance with the currently approved protocol and any other study agreements, ICH GCP, and all applicable regulatory requirements.

Records and documents, including signed ICFs, pertaining to the conduct of this study must be retained by the Investigator for at least 2 years after the last marketing application approval or 2 years after formal discontinuation of the clinical development of the investigational product or according to applicable regulatory requirement(s). If the Investigator withdraws from the responsibility of keeping the study records, custody must be transferred to a person willing to accept the responsibility. The Sponsor must be notified immediately by telephone or e-mail and the notification confirmed in writing if a custodial change occurs.

#### 10.4.7 Source Documents

Source documents provide evidence for the existence of the patient and substantiate the integrity of the data collected. Source documents are filed at the Investigator's site.

Data entered in the eCRF that are transcribed from source documents must be consistent with the source documents or the discrepancies must be explained. The Investigator may need to request previous medical records or transfer records, depending on the study. Also, current medical records must be available.

Any electronic study data are to be entered into a secure, validated data processing system and a backup maintained. Any changes to electronic study data will be documented.

#### 10.4.8 Study and Site Closure

The Sponsor designee reserves the right to close a study site or terminate the study at any time for any reason at the sole discretion of the Sponsor. Study sites will be closed upon study completion. A study site is considered closed when all required documents and study supplies have been collected and a study-site closure visit has been performed.

The Investigator may initiate study-site closure at any time, provided there is reasonable cause and sufficient notice is given in advance of the intended termination.

Reasons for the early closure of a study site by the Sponsor or Investigator may include but are not limited to:

- Failure of the Investigator to comply with the protocol, the requirements of the IRB or local health authorities, the Sponsor's procedures, or GCP guidelines.
- Inadequate recruitment of participants by the Investigator.

- Discontinuation of further study drug development.

#### 10.4.9 Publication Policy

All information regarding study drug supplied by the Sponsor to the Investigator or generated as a result of any clinical studies is privileged and confidential information belonging to the Sponsor. The Investigator agrees to use Sponsor's confidential information solely to accomplish the study and will not use such information for any other purposes without the prior written consent of I-Mab. It is understood that there is an obligation to provide the Sponsor with complete and accurate data obtained during the study. The information obtained from the clinical study will be used towards the development of study drug and may be disclosed by I-Mab to regulatory authority(ies), other Investigators, corporate partners, or consultants as required.

It is anticipated that the results of this study may be presented at scientific meetings and/or published in a peer reviewed scientific or medical journal. A Publications Committee, comprised of Investigators participating in the study and representatives from I-Mab as appropriate, will be formed to oversee any publication or presentation of the study results, which will reflect the experience of all participating study centers. All publications and presentations must be approved in advance by I-Mab, in its sole discretion. Subsequently, individual Investigators may publish results from the study in compliance with their agreement with the Sponsor.

A pre-publication manuscript is to be provided to I-Mab at least 30 days prior to the submission of the manuscript to a publisher. Similarly, the Sponsor will provide any company-prepared manuscript to the Investigators for review at least 30 days prior to submission to a publisher. All publications and presentations must be approved in writing by I-Mab before public disclosure.

Authorship will be determined by mutual agreement and in line with International Committee of Medical Journal Editors authorship requirements.

## 10.5 Clinical Laboratory Tests

The tests detailed in [Table 11](#) will be performed by the local/central laboratory. Investigators must document their review of each laboratory safety report.

Protocol-specific laboratory requirements for inclusion or exclusion of participants are detailed in [Section 5](#) of the protocol.

Additional tests may be performed at any time during the study as determined necessary by the Investigator or required by local regulations.

**Table 11: Protocol-Required Safety Laboratory Assessments**

Laboratory Assessments	Parameters	
Hematology	WBC count with differential	Red blood cell count and reticulocytes
	Platelet count	Hemoglobin
	Mean corpuscular hemoglobin	Hematocrit
	Mean corpuscular volume	Absolute neutrophil count
HBV, HCB, HIV (Screening Only)	Anti-hepatitis B surface antibody	HIV-1
	HBsAg	HIV-2
	Anti-HCV	
Coagulation Studies	International normalized ratio (INR)	
	Prothrombin time	
	Activated partial thromboplastin time or	
	Partial thromboplastin time	
Serum Chemistry	Alanine aminotransferase (ALT)	Bicarbonate
	Aspartate aminotransferase (AST)	Glucose
	Amylase	Lipase
	Albumin	Phosphorus
	Alkaline phosphatase	Total bilirubin
	Blood urea nitrogen	Total protein
	Calcium	Magnesium
	Cholesterol	Potassium
	Creatinine	Chloride
	Gamma-glutamyl transferase	CA125 (ovarian cohorts only)
	Lactate dehydrogenase	Uric Acid
	Sodium	
Urinalysis	A dipstick urinalysis is to be performed for:	
	Color	Protein
	pH	Glucose
	Specific gravity	Ketones
	Blood	

Laboratory Assessments	Parameters
	If dipstick findings are abnormal, a microscopic examination is to be performed
Pregnancy Testing	Serum pregnancy test at Screening, Cycle 1 Day 1 (within 72 hours prior), Cycle 4 Day 1 and Day 1 of every subsequent 4 cycles (i.e., Cycle 8 Day 1, Cycle 12 Day 1, etc.). The screening serum pregnancy test can be used as the test prior to Day 1 study treatment if it is performed within the prior 72 hours. Additional tests may be ordered at the Investigator's discretion. Positive urine test should be confirmed with a serum pregnancy test. Follicle stimulating hormone (FSH) test is required for postmenopausal women only.

## 10.6 Contraceptive Guidance

### 10.6.1 Definitions

#### 10.6.1.1 Females of Childbearing Potential

A woman is considered fertile following menarche and until becoming post-menopausal unless permanently sterile. Permanent sterilization methods include hysterectomy, bilateral salpingectomy, and bilateral oophorectomy.

#### 10.6.1.2 Postmenopausal Female

A postmenopausal state is defined as no menses for 12 months without an alternative medical cause. A high follicle-stimulating hormone (FSH) level in the postmenopausal range may be used to confirm a postmenopausal state in women not using hormonal contraception or hormonal replacement therapy (HRT). However, in the absence of 12 months of amenorrhea, confirmation with more than one FSH measurement >40 IU/L is required.

Females on HRT whose menopausal status is not confirmed will be required to use one of the non-estrogen hormonal highly effective contraception methods if they wish to continue their HRT during the study. Otherwise, they must discontinue HRT to allow confirmation of postmenopausal status before study enrollment.

### 10.6.2 Fertile Males

A man is considered fertile after puberty (Tanner Stage II) unless permanently sterile by bilateral orchidectomy or vasectomy with medical assessment of surgical success.

### 10.6.3 Highly Effective Contraception

Methods that can achieve a failure rate of less than 1% per year when used consistently and correctly are considered as highly effective birth control methods ([Clinical Trials Facilitation Group 2014](#)). Such methods include:

- Combined (estrogen and progestin containing) hormonal contraception associated with inhibition of ovulation (oral, intravaginal, transdermal).
- Progestin-only hormonal contraception associated with inhibition of ovulation (oral, injectable, implantable).
- Intrauterine device.
- Intrauterine hormone-releasing system.
- Bilateral tubal occlusion.
- Vasectomized partner, provided that partner is the sole sexual partner of the female study participant and that the vasectomized partner has received medical assessment of the surgical success.

- Sexual abstinence- only if defined as refraining from heterosexual intercourse during the entire period of risk associated with the study treatments. The reliability of sexual abstinence needs to be evaluated in relation to the duration of the clinical study and the preferred and usual lifestyle of the patient.

#### 10.6.4 Acceptable Birth Control Methods that are not Highly Effective Contraception

Acceptable birth control methods that result in a failure rate of more than 1% per year include:

- Progestin-only oral hormonal contraception, where inhibition of ovulation is not the primary mode of action.
- Male or female condom with or without spermicide.
- Cap, diaphragm, or sponge with spermicide.

A combination of male condom with either cap, diaphragm, or sponge with spermicide (double barrier methods) are also acceptable, but not highly effective, birth control methods.

#### 10.6.5 Unacceptable Contraception Methods

- Periodic abstinence (calendar, symptothermal, post-ovulation methods).
- Withdrawal (coitus interruptus).
- Spermicides only.
- Lactational amenorrhea method.
- Combination of male and female condoms.

#### 10.6.6 Female Contraception Guidance

Females of childbearing potential (FOCBP) may only be enrolled after confirming a negative highly sensitive serum pregnancy test during Screening and a urine or serum pregnancy test within 72 hours prior to receiving the first study drug administration.

It is required that FOCBP agree to use at least 2 effective contraceptive methods (1 highly effective method in combination with a barrier method; oral, injectable, or implantable hormonal contraceptive; tubal ligation; intra-uterine device; barrier contraceptive with spermicide; or vasectomized partner), one of which must be barrier, from signing the ICF date of ICF signature, throughout the study, and for up to 5 months following the last dose of TJ004309.

#### 10.6.7 Male Contraception Guidance

Males must agree to use a condom (a latex condom is recommended) during sexual contact with a pregnant female or a female of childbearing potential and will avoid donation of sperm or having a female partner conceive from the time of date of ICF signature, while participating in the study, during dose interruptions, and for at least 5 months after the last dose of study

treatment, even if he has undergone a successful vasectomy. Consider contraception for the FOCBP partner.

#### 10.6.8 Collection of Pregnancy Information

Pregnancy testing should be performed at monthly intervals in female participants. Female partners of male patients are also recommended to have pregnancy testing performed at monthly intervals.

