Abbreviations: ALT = alanine aminotransferase; aPTT = activated partial thromboplastin time; AST = aspartate aminotransferase;; ECG = electrocardiogram; ECOG = Eastern Cooperative Oncology Group; EOI = end of infusion; HBsAg = hepatitis B surface antigen; HCV = hepatitis C virus; HIV = human immunodeficiency virus; INR = international normalized ratio; NCI CTCAE = National Cancer Institute Common Terminology Criteria for Adverse Events; PTT = partial thromboplastin time.

- a) Treatment with TJ004309 may continue in accordance with the protocol. Subsequent study cycles should follow the same schedule of assessments as Cycle 2 unless otherwise specified.
- b) Relevant medical history including current disease state and prior treatment, including last prior therapy, best response to last prior therapy (partial response, complete response, stable disease, or progressive disease), and either time on last therapy or duration of response. Medical history includes all clinically significant diseases, cardiac history, surgeries, cancer history (which may include, but not limited to prior cancer therapies, procedures, and estrogen receptor and progesterone receptor status, bulky disease status), reproductive status, smoking history, use of alcohol and drugs of abuse.
- c) Anti-hepatitis B surface antibody, HBsAg, anti-HCV, HIV-1 and HIV-2 antibodies at Screening only.
- d) Serum pregnancy test at Screening, urine pregnancy at pre-dose Cycle 1 Day 1 (within 72 hours prior), Cycle 4 Day 1 and Day 1 of every subsequent 4 cycles (i.e., Cycle 8 Day 1, Cycle 12 Day 1, etc.). The screening serum pregnancy test can be used as the test prior to Day 1 study treatment if it is performed within the prior 72 hours. Additional tests may be ordered at the Investigator's discretion. Positive urine pregnancy tests should be confirmed with a serum pregnancy test. Only a Follicle-stimulating hormone test is required for postmenopausal women.
- e) Samples may be collected for genetic testing (i.e., MSI/dMMR, BRCA, HRD, etc) if not previously obtained. Ovarian cancer patients only.
- f) Archival tissue is required for both Cohorts 1 and 2. Blocks are preferred but archival tumor tissue that allows the preparation of at least 20 slides prior to study entry is acceptable as well. See lab manual for further instructions. Format of archival tissue is at the site's discretion. Sponsor may request PD-L1 testing at central laboratory.

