### 4.5 Safety Follow-up Period

After the treatment periods, all subjects will enter a safety follow-up period and will be evaluated for safety, tolerability, and tumor response (if applicable) for at least 90 days after the last dose of study drug, or 30 days following cessation of study treatment if the subject initiates new anticancer therapy, whichever is earlier. Subjects will be required to return to the study sites for three (3) safety follow-up visits (approximately 30, 60 and 90 days after the last dose of study drug), except those subjects who withdraw consent for study participation. After treatment discontinuation, in the event of continuing serious adverse events (SAEs), subjects will be followed until resolution or stabilization of the SAEs (regardless of the relationship to the IMP). Any subject who has an ongoing non-serious AE that is possibly related or related to the IMP or study procedures at the 90-day post-treatment Follow-up visit will be followed up, where possible, until resolution or until the unresolved non-serious AE is judged by the Investigator (or designee) to have stabilized. Any subject who has an ongoing non-serious AE that is not related or unlikely related to the IMP or study procedures at the Follow-up visit, can be closed out as ongoing at the Investigator's discretion. If a subject initiates a new anticancer therapy within 30 days after the last dose of study treatment, one (1) Post-Treatment Safety Follow-Up visit should occur approximately 30 days after the last dose of study drug and therefore subsequent follow-up visits will not be required.

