- a. Agree to use at least 2 effective contraceptive methods (1 highly effective method in combination with a barrier method; oral, injectable, or implantable hormonal contraceptive; tubal ligation; intra-uterine device; barrier contraceptive with spermicide; or vasectomized partner), one of which must be barrier. Use of contraceptive methods lasts from date of ICF signature, throughout the study, and for up to 5 months following the last dose of TJ004309.
- b. Have a negative serum pregnancy test (sensitive of at least 25 mIU/ml) at Screening; and have a negative serum or urine pregnancy test within 72 hours prior to Cycle 1 Day 1 of study treatment (note that the screening serum pregnancy test can be used as the test prior to Day 1 study treatment if it is performed within the prior 72 hours)
- c. Avoid conceiving for 5 months after the last dose of TJ004309
- d. Avoid donation of ova from date of ICF signature until 5 months after the last dose of TJ004309
- e. Agree to ongoing urine pregnancy testing, if clinically indicated, during the study

16. Males must agree to use a condom (a latex condom is recommended) during sexual contact with a pregnant female or a female of childbearing potential, will avoid donation of sperm, or having a female partner conceive from date of ICF signature, while participating in the study, during dose interruptions, and for at least 5 months after the last dose of study treatment, even if he has undergone a successful vasectomy.

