## 8 STUDY ASSESSMENTS AND PROCEDURES

Study procedures and their timing are summarized in the SoA ([Table 2](#) and [Table 3](#)).

Immediate safety concerns should be discussed with the Sponsor immediately upon occurrence or awareness to determine if the patient should continue or discontinue study drug.

Adherence to the study design requirements, including those specified in the SoA, is essential and required for study conduct.

All screening evaluations must be completed and reviewed to confirm that a potential patient meets all eligibility criteria. The Investigator will maintain a screening log to record details of all participants screened and to confirm eligibility or record reasons for screening failure, as applicable.

The patient/patient's health proxy must provide written informed consent before the performance of any study-specific procedures.

Procedures conducted as part of the patient's routine clinical management (e.g., blood count) and obtained before signing of the informed consent form (ICF) may be utilized for screening or baseline purposes provided the procedures met the protocol-specified criteria and were performed within the time frame defined in the SoA ([Table 2](#)).

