### 8.2.7 Clinical Safety Laboratory Assessments

See [Section 10.5](#) for the list of clinical laboratory tests to be performed and the SoA ([Table 2](#)) for the timing and frequency. Additional clinical laboratory evaluations will be performed at other times if judged to be clinically appropriate or if the ongoing review of the data suggests a more detailed assessment of clinical laboratory safety evaluations is required (e.g., repeat testing as required to confirm results).

The Investigator must review the laboratory reports, document this review, and record any clinically relevant changes occurring during the study in the AE section of the eCRF. The laboratory reports must be filed with the source documents. Clinically significant abnormal laboratory findings are those which are not associated with the underlying disease, unless judged by the Investigator to be more severe than expected for the patient's condition.

If such values do not return to normal/baseline within a period of time judged reasonable by the Investigator, the etiology should be identified, and the Sponsor notified.

All protocol-required laboratory assessments, as defined in [Section 10.5](#), must be conducted in accordance with the laboratory manual and the SoA.

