#### 8.4.8 Pregnancy Reporting Requirement

A pregnancy event refers to a pregnancy of a female subject or a maternal pregnancy of a male patient during a clinical study or within 5 months after the patient's last dose of study drug. The Investigator will collect pregnancy information via the Pregnancy Reporting Form within 24 hours after becoming aware of the information.

Study drug must be discontinued immediately in the event of a pregnancy in a patient. The patient should be referred to an obstetrician/gynecologist experienced in reproductive toxicity for further evaluation and counseling.

The Investigator will follow the patient /patient's partner until completion of the pregnancy and provide this follow-up information using the same procedures as the initial reporting. Generally, the follow-up will be within 6 to 8 weeks following the estimated delivery date. Any termination of the pregnancy will be reported regardless of fetal status (presence or absence of anomalies) or indication for the procedure.

If the outcome of the pregnancy meets the criteria for immediate classification as an SAE ([Section 8.3.2](#)), then the Investigator should report it as such, and the Investigator needs to fill out an SAE reporting form and report to the Sponsor within 24 hours. Furthermore, all neonatal deaths that occurs within 30 days of birth should be reported, without regard to causality, as SAEs. In addition, any infant death after 30 days that the Investigator suspects is related to the in-utero exposure to the study drug should also be reported.

While pregnancy itself is not considered to be an AE or SAE, any pregnancy complication or elective termination of a pregnancy will be reported as an AE or SAE.

Any post-study pregnancy related SAE considered reasonably related to the study drug by the Investigator will be reported to the Sponsor or designee. While the Investigator is not obligated to actively seek this information in former study participants, he or she may learn of an SAE through spontaneous reporting.

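### Section 10.6.8 asks for monthly pregnancy tests, but the on-treatment schedule leaves nominal gaps of 63 and then 84 days

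*Protocol*

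**What the plan says.** Protocol Section 10.6.8 sets a frequency: "Pregnancy testing should be performed at monthly intervals in female participants". It gives no end date and does not restrict the statement to women of childbearing potential.

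The schedule sets a different frequency. The Pregnancy Test row of Table 2 (Section 1.2) marks Screening, Cycle 1 Day 1, every fourth cycle and End of Treatment. The three follow-up columns are blank. Footnote d lists Screening and Cycle 1 Day 1, then "Cycle 4 Day 1 and Day 1 of every subsequent 4 cycles (i.e., Cycle 8 Day 1, Cycle 12 Day 1, etc". Table 11 (Section 10.5) has the same cycles: "Serum pregnancy test at Screening, Cycle 1 Day 1 (within 72 hours prior), Cycle 4 Day 1", then every four cycles. Footnote d and Table 11 both leave further tests to the investigator's discretion.

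Two passages give the schedule its force. Section 8 says: "Adherence to the study design requirements, including those specified in the SoA, is essential and required for study conduct". Section 8.2.7 says the laboratory assessments defined in Section 10.5, which include pregnancy testing, "must be conducted in accordance with the laboratory manual and the SoA".

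Sections 8.4.8 and 10.6.8.1 require study drug to be stopped immediately if a participant becomes pregnant.

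**The concern.** The protocol gives two frequencies for one safety procedure, and they cannot both describe routine practice. A site working from Table 2 will test about every two to three months while Section 10.6.8 asks for monthly tests. Neither the site nor a monitor can tell whether an untested month is a deviation.

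What is at stake is participant safety. The duty to stop treatment on pregnancy depends on detecting it. When tests are further apart, more infusions can be given to a woman who is already pregnant. The statistical analysis is not touched.

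**Working it through.** The plan states no gap length, so there is no figure to reproduce. The check is calendar arithmetic.

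**Inputs**
- Cycle length: 21 days (Section 4.1).
- Scheduled on-treatment tests: Day 1 of Cycles 1, 4, 8, 12 and so on (Table 2, footnote d, Table 11).
- Visit window: none at Cycle 1 Day 1, ±2 days from Cycle 2 (Table 2).
- Infusions: Day 1 of every cycle.
- A month is taken as 28 to 30.4 days (assumption).

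**Gaps.** Day 1 of cycle c falls on study day (c − 1) × 21 + 1.
- Cycle 1: Day 1. Cycle 4: Day 64. Cycle 8: Day 148. Cycle 12: Day 232.
- First gap: 64 − 1 = 63 days. Later gaps: 148 − 64 = 84 and 232 − 148 = 84 days.
- With the visit window: 63 ± 2 = 61 to 65 days, and 84 ± 4 = 80 to 88 days.
- Relative to a month: 63/30.4 = 2.1 to 63/28 = 2.25; 84/30.4 = 2.8 to 84/28 = 3.0.

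The gaps are nominal. Dose delays lengthen them, and an End of Treatment visit before the next scheduled test shortens the last one.

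**Infusions between tests.** Take a pregnancy arising just after a test day, ignoring the time a test needs to turn positive.
- Current schedule, after Cycle 1 Day 1: Cycles 2 and 3, so 2 infusions before the next test.
- Current schedule, after Cycle 4 Day 1: Cycles 5, 6 and 7, so 3 infusions. The same holds for later gaps.
- Monthly testing with 21-day dosing: a 28-day interval starting at Cycle 1 Day 1 has tests on Days 1, 29, 57 and 85 and infusions on Days 22, 43 and 64, so 1 infusion per interval. At 30.4 days the tests fall on about Days 1, 31, 62 and 92, and the interval from Day 62 to Day 92 contains two infusions (Days 64 and 85). Monthly testing therefore lets through 1, sometimes 2.
- Excess due to the schedule: first gap 2 − 1 = 1; later gaps 3 − 2 = 1 to 3 − 1 = 2. A pregnancy arising late in a gap may meet no extra infusion.
- A test before dosing on Day 1 of every cycle: no infusion falls between tests, on the same assumption.

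**Extra on-treatment tests if every cycle is tested**
- 4 cycles (84 days): Cycles 2–4 = 3, against Cycle 4 = 1; 2 extra.
- 182 days (assumed 6 months): Cycles 2–9 = 8, against Cycles 4 and 8 = 2; 6 extra.
- 364 days (assumed 12 months): Cycles 2–18 = 17, against Cycles 4, 8, 12 and 16 = 4; 13 extra.

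**Which visit interval fits.** 21 days is within a month; every second cycle, 2 × 21 = 42 days, is not.

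**The case against.** The best defence is that Section 10.6.8 says should, and its next sentence only recommends testing of partners. It can be read as guidance, with Table 2 as a minimum that the investigator may supplement. That softens the obligation but leaves the inconsistency: discretion sets no interval, and the schedule that sites must follow does not produce the recommended frequency.

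A second defence is that editing one sentence of Section 10.6.8 to match the schedule would also remove the conflict. It would. The choice is partly clinical. Testing each cycle is preferred here because treatment must stop on pregnancy and the visits already take place.

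Three stronger readings are tempting, and the documents do not support them.
- A reader might infer that the lack of tests after End of Treatment contradicts the 5-month window. Section 8.4.8 defines a reportable pregnancy as one "during a clinical study or within 5 months after" the last dose, but this is a reporting duty triggered by awareness. Neither it nor the 5-month contraception rule requires testing, and Section 10.6.8 gives no end date.
- Inclusion criterion 15e ("Agree to ongoing urine pregnancy testing, if clinically indicated, during the study") might look like a third testing rule. It sets no interval. It is the participant's agreement to extra testing and is compatible with footnote d.
- The 2 or 3 infusions between scheduled tests might be charged wholly to the schedule. Monthly testing would itself let through 1, sometimes 2.

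**Conclusion.** The point holds as an on-treatment inconsistency. Section 10.6.8 recommends monthly testing, and Table 2, footnote d and Table 11 deliver it at nominal gaps of 63 and then 84 days. The worst-case consequence is roughly 1 to 2 more infusions before a scheduled test than under monthly testing.

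The gaps follow directly from the documents. The infusion figure assumes a pregnancy arising soon after a test, dosing on time and a month of 28 to 30.4 days. The number of women of childbearing potential is not given, and they must use two contraceptive methods, so the expected number of affected pregnancies cannot be sized.

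This is a minor, worthwhile correction. The SAP (Section 4.1) reports that Part 2 was not initiated, so the benefit is to any women still on treatment and to any later protocol that reuses this text.

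**What to change.** **Change.** For women of childbearing potential, amend the Table 2 row, footnote d and Table 11 to a urine test before dosing on Day 1 of every 21-day cycle, with serum confirmation of a positive result. Keep the existing Screening and End of Treatment tests. Label the on-treatment tests in Table 11 as urine; it now calls them serum, while footnote d calls the Cycle 1 Day 1 test urine. Limit Section 10.6.8 to women of childbearing potential, since footnote d asks only for a follicle-stimulating hormone test in postmenopausal women.

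**Cost.** One amendment to a table row, a footnote, a Table 11 cell and Section 10.6.8. Per woman, it adds 2 urine tests over 4 cycles, 6 over an assumed 6 months or 13 over an assumed 12 months. Table 2 already schedules urinalysis at these visits, so none is added. Testing every cycle is somewhat more frequent than monthly, but it fits the visits; every second cycle would not meet the monthly interval.

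**Optional, and not the correction of a contradiction.** Section 4.5 already provides "three (3) safety follow-up visits (approximately 30, 60 and 90 days after the last dose of study drug"). A urine test could be added at each, with Section 10.6.8 stating that the interval ends at the last scheduled follow-up visit. That is up to 3 more tests, or 1 if new anticancer therapy starts within 30 days of the last dose. If testing is meant to run to 5 months (about 152 days, so about 5 monthly tests), the month 4 and 5 tests have no visit. They must then be written into the schedule as home or local tests; otherwise the amendment would create a new mismatch.
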